#### Dose escalation period

During the dose escalation period a dose adjustment may only occur at Visit 16, 18, 20, 22 and 24. If a patient experiences tolerance issues with a dose due to AEs over the last two weeks before a remote visit (i.e., Visit 16, 20 or 24) and believes that a dose adjustment is needed, the patient will be asked to come to the site and to return the unused trial medication dispensed to him/ her during the previous site visit. The Investigator will assess together with the patient, if a dose adjustment is needed, and a new trial medication will be dispensed to the patient for the next two administrations.

If a patient experiences tolerance issues with a dose due to AEs over two weeks within the treatment period before Visit 14, the trial medication should be discontinued, and the patient should undergo the procedures of the EOT and Follow-up visit (Visit 32 and 33 resp.).

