6.3 SUBJECT SETS ANALYSED

The following analysis sets will be defined:

Screened Set

The screened set (SS) includes all patients for whom a signed informed consent is available at the time of final DBL. It will be used only for display of patient disposition.

Randomised Set

The randomised set (RS) includes all screened patients who were randomised in the trial, regardless of whether any study drug was taken. It will be used only for display of patient disposition and IPDs.

Treatment assignment will be as randomised (i.e. planned maintenance treatment).

Treated Set

The treated set (TS) is defined as all randomised patients who received at least one dose of study treatment.

The TS will be used for presentation of demographic/baseline data, concomitant medications/diagnoses, treatment exposure, efficacy and safety.

Treatment assignment will be according to both actual maintenance treatment and planned maintenance treatment (i.e. as randomised), depending on the analysis.

It is not expected on the database that the situation in which a patient could be treated without randomisation will exist. Documentation is in place by the Interactive Response Technology (IRT) vendor, which states that, should any patient be given treatment at the site in error

without randomisation, such a patient will be subsequently randomised to a treatment which is not incompatible with the one given in error.

Full Analysis Set

The full analysis set (FAS) was defined in the CTP in the same way as TS. Since the definitions are the same, the TS label will be retained for both efficacy and safety analysis, and the FAS label will not be used.

Per Protocol Set

A per protocol set (PPS) will not be defined in this study.

[REDACTED]

[figure not shown]
[REDACTED]

The table below summarises the analysis sets and their main intended purpose [REDACTED]

[REDACTED]

Table 6.3: 1 Subject sets analysed

| Data type | Analysis set | | | |
|--|--------------|----|----|---|
| | SS | RS | TS | █ |
| Disposition | X | X | | |
| Demographic and baseline characteristics | | | X | |
| Concomitant diseases and medications | | | X | |
| Exposure to study drug | | | X | |
| Primary efficacy endpoint | | | X | |
| Secondary efficacy endpoints | | | X | |
| █ | | | █ | |
| █ | | | █ | |
| Adverse events | | | X | |
| Vital signs | | | X | |
| Laboratory safety data | | | X | |
| 12-lead ECG | | | X | |
| Other safety | | | X | |
| █ | | | | █ |

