7. PLANNED ANALYSIS

Descriptive statistics for continuous variables will generally include N (number of patients with non-missing values), arithmetic mean, standard deviation (SD), minimum, Q1 (lower quartile), median, Q3 (upper quartile) and maximum. In general, means, medians, other quartiles and SDs will be presented to one more decimal place than the raw data. Minimums and maximums will be presented to the same number of decimal places as the raw data.

Tabulations of frequencies for categorical data will include all possible non-missing categories unless otherwise specified, and will display the number of patients in a category as well as the percentage (%) relative to the respective treatment group. Percentages will be rounded to one decimal place. A missing category will be displayed only if there are actually missing values. Percentages will be based on all patients in the respective patient set whether they have non-missing values or not.

Disposition

The disposition of patients will be displayed. This table will present the number of patients enrolled, randomised and treated. The number treated will be further presented separating the dose escalation and maintenance periods. Planned maintenance treatment (see [Section 6.1.2](#)) will be used for this table.

The number of patients who completed or who prematurely discontinued study treatment will be summarised, along with the categorization of the primary reason for treatment discontinuation. The number of patients and reasons for prematurely discontinuing treatment will also be displayed separately for the dose escalation and maintenance periods.

The number of patients who completed or who prematurely withdrew from the study will be summarised, along with the categorization of the primary reason for study withdrawal. It should be noted that in this study, a patient is considered to have completed the study if all scheduled safety follow-up procedures have been performed for that patient, including for patients who discontinued treatment early. In other words, a patient may complete this study without completing treatment.

Where shown on the disposition table, the percentages will be of the number of patients treated in each treatment group.

Kaplan-Meier estimates will be presented graphically by planned maintenance treatment group for time to early treatment discontinuation (defined as *treatment discontinuation date*

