7.8 SAFETY ANALYSIS

All safety analyses will be performed on the TS, including only on-treatment data (unless otherwise specified in [Section 7.8.1](#)). No hypothesis testing is planned for safety.

All specified summaries and analysis will be presented for both actual maintenance treatment and planned maintenance treatment.

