7.8.1 Adverse Events

The analyses of adverse events will be descriptive in nature. All analyses of AEs will be based on the number of patients with AEs and not on the number of AEs.

The analysis of adverse events will be based on the concept of treatment emergent adverse events. AEs will be considered “on-treatment” if the AE start date meets the 28-day REP criterion (see [Section 6.1.6](#)). AEs occurring prior to the start of treatment will be assigned to “screening”. AEs occurring more than 28 days after the last dose of study treatment will be assigned to “follow-up”. Unless otherwise specified, on-treatment AEs will be pooled across dose escalation and maintenance periods.

An overall summary of adverse events will be presented for all patients in the TS. This summary will show the number and percent of patients with any AE, any investigator defined drug-related AE, any AE leading to the discontinuation of study medication, any AESI (as determined by the investigator), any serious AE (including reason for serious (death, life-threatening, disability/permanent damage, required or prolonged hospitalization, congenital anomaly/birth defect and other medically important events)), and any drug-related serious AE. The overall summary will be presented with the treatment period pooled across, and split into, dose escalation and maintenance periods, respectively.

AEs will be coded using the version of the MedDRA coding dictionary in force at final DBL. The frequency of patients with all AEs will be summarised by treatment, primary system organ class (SOC) and preferred term (PT). A patient with multiple on-treatment occurrences of the same preferred term meeting the criteria for inclusion in the table will be counted only once in these tabulations. SOC's will be sorted by descending overall frequency; PT's will be sorted by descending overall frequency (within SOC). The summary of all AEs will be presented with the treatment period pooled across, and split into, dose escalation and maintenance periods, respectively.

The AE summary by primary SOC and PT will also be repeated for each of the following, with the treatment period pooled across dose escalation and maintenance periods, only:

- AEs leading to treatment discontinuation
- Serious AEs
- Investigator-defined drug-related AEs
- Drug-related serious AEs.

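### Maintenance-period AE percentages use the whole Treated Set as denominator, so patients who stopped during dose escalation dilute them, by an amount that differs by arm and between the planned and actual versions of the table

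*SAP*

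**What the plan says.** SAP 7.8 fixes the population: "All safety analyses will be performed on the TS, including only on-treatment data". SAP 6.3 defines it: "The treated set (TS) is defined as all randomised patients who received at least one dose of study treatment". Anyone who stopped during escalation is therefore included. Table 6.3:1 assigns adverse events to this set, and no visible set is limited to patients who entered maintenance.

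SAP 7.8.1 then states "An overall summary of adverse events will be presented for all patients in the TS" and splits that table by period: "The overall summary will be presented with the treatment period pooled across, and split into, dose escalation and maintenance periods, respectively". The SOC/PT table follows: "The summary of all AEs will be presented with the treatment period pooled across, and split into, dose escalation and maintenance periods, respectively". The general rule for frequency tables in SAP 7 is "Percentages will be based on all patients in the respective patient set whether they have non-missing values or not".

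Three other provisions matter:
- SAP 7.8 requires every safety table by both actual and planned maintenance treatment.
- SAP 6.1.3 (Table 6.1.3:1) places an active-arm patient who stops during escalation in the next maintenance dose up. A stop at 0.3–2.4 mg counts as 2.4 mg, a stop above 2.4 and up to 4.8 mg as 4.8 mg, and only a stop above 4.8 mg as 6.0 mg.
- On safety windows, SAP 7.8.1 says "AEs will be considered “on-treatment” if the AE start date meets the 28-day REP criterion", so on-treatment time ends 28 days after the last dose.

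**The concern.** A patient who leaves before Visit 26 (Week 24) adds one to the maintenance denominator and almost nothing to its numerator. The maintenance columns then show the share of all treated patients who had a maintenance-period event. A reader is likely to take this as the event risk among patients in maintenance.

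Escalation stops are built into the design and could plausibly differ by arm. Protocol 4.1.2 says that for dose intolerance due to AEs "over two weeks within the treatment period before Visit 14, the trial medication should be discontinued". Protocol 1.4.2 calls the expected side effects dose dependent, and Protocol 1.2 reports nausea in up to 70% on drug versus 23% on placebo in the earlier multiple-dose trial.

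The display is relevant to dose choice. Protocol 1.4.2 describes GI disorders as temporary and gives tolerability an essential part in dose finding. SAP 7.4.1 says that tolerability and safety will be weighed in choosing the Phase 3 dose. A comparison of escalation with maintenance AE rates is a natural place to look for adaptation.

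**Working it through.** **Denominator.** SAP 7.8.1 names no denominator for the period columns. SAP 7 bases percentages on the whole patient set, SAP 7.8 and Table 6.3:1 make that set the Treated Set, and nothing visible overrides this. Where the SAP wants entrants only, it says so: the first-versus-last maintenance dose shift table in SAP 7 is limited to patients who reached maintenance.

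**Formula.** Let r be the AE rate among patients who entered maintenance and d the share of the group that stopped during escalation. Ignoring the few residual-effect-period events after Week 24,

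displayed rate = r × (1 − d).

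The plan states no AE rate, escalation drop-out rate or maintenance N, so there is no figure of its own to reproduce. N = 60 per group is from Protocol 7.5; every r and d below is an assumption.

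**By planned treatment, equal rates among entrants (r = 50%).**
- Placebo, d = 5%: 0.50 × 0.95 = 47.5%.
- High-dose arm, d = 15%: 0.50 × 0.85 = 42.5%, a gap of 5 points.
- d = 25%: 0.50 × 0.75 = 37.5%, a gap of 10 points.
- d = 35%: 0.50 × 0.65 = 32.5%, a gap of 15 points.

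A real excess can also be hidden. With placebo r = 50%, d = 5% and active r = 70%, d = 30%, the table shows 47.5% versus 0.70 × 0.70 = 49.0%. The gap is 1.5 points where the entrants differ by 20.

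**By actual treatment.** Table 4.1.4:1 of the protocol schedules no active dose above 2.4 mg through Visit 13, so an active-arm stop before Visit 14 on the scheduled dose counts as 2.4 mg. Doses above 4.8 mg are first scheduled at Visit 22, so few escalation stops can count as 6.0 mg.

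Assume escalation stops of 9, 15 and 18 in the planned 2.4, 4.8 and 6.0 mg arms (3 on placebo), and that all others enter maintenance at their planned dose. Half of the 4.8 and 6.0 mg stops (8 and 9) fall before Visit 14, and the later 6.0 mg stops are at 3.0–4.8 mg. Then:
- 2.4 mg: N = 60 + 8 + 9 = 77; stops = 9 + 8 + 9 = 26.
- 4.8 mg: N = 60 − 8 + 9 = 61; stops = 7 + 9 = 16.
- 6.0 mg: N = 60 − 18 = 42; stops = 0.

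With r = 60% in every group, the same trial gives:

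| Group | By planned treatment | By actual treatment |
|---|---|---|
| Placebo | 0.60 × 57/60 = 57.0% | 57.0% |
| 2.4 mg | 0.60 × 51/60 = 51.0% | 0.60 × 51/77 = 39.7% |
| 4.8 mg | 0.60 × 45/60 = 45.0% | 0.60 × 45/61 = 44.3% |
| 6.0 mg | 0.60 × 42/60 = 42.0% | 0.60 × 42/42 = 60.0% |

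Across the active doses the planned version falls with dose and the actual version rises, although entrants have the same rate throughout. If all the 4.8 and 6.0 mg stops fall before Visit 14, the actual version shows 32.9% (0.60 × 51/93), 60.0% and 60.0%.

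**Residual effect period.** A last dose at Visit 22 (Day 141) has an on-treatment window to Day 141 + 28 = 169, the planned day of Visit 26. A patient stopping at Visits 22–25 can therefore have an on-treatment event on or after Week 24. SAP 6.1.1 defines the phases for a patient who stays on treatment as planned, so the period of such an event is not defined.

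**The case against.** - **The denominator is inferred.** The split sentences name none, the general rule in SAP 7 is worded around missing values, and Protocol 7.2.5 refers to sponsor standard tables that are not in the documents. A different house convention is possible. It is not written in the SAP, and the visible rules lead to the Treated Set.
- **The Treated Set percentage is a valid quantity.** It is the share of all treated patients with a maintenance-period event. An entrants-only rate conditions on having completed escalation, a selection after randomisation that may flatter an arm which lost its least tolerant patients. This stands, and is why the new columns need a footnote and the other columns should stay on the Treated Set.
- **The entrants can be recovered.** Disposition gives numbers treated by period for planned treatment, and the maintenance-dose shift table essentially gives entrants by starting dose. This also stands and limits the harm, but it leaves the rescaling to the reader. The exposure-adjusted AE table does not help: it has no period split, and its time at risk starts at first dose.
- **Stronger readings go too far.** A reader might infer that escalation stoppers cannot have a maintenance event; the 28-day window allows a few. A reader might also infer that the tables always flatter the higher doses. By actual treatment the 2.4 mg column is probably diluted most and 6.0 mg hardly at all, so the top dose can look worse than the lower ones.

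**Conclusion.** The point holds. Followed as written, the SAP multiplies each maintenance-period AE percentage by about one minus that group's share of escalation stops, and this share can differ between groups and between the planned and actual versions. Under the assumed 5% versus 15–35% stops and a 50% rate among entrants, the artefact by planned treatment is 5 to 15 points. By actual treatment its direction across doses can reverse. The mechanism follows from the text; the size rests wholly on assumed drop-out and event rates.

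The impact is limited. Safety is descriptive with no testing, only the maintenance columns of two AE tables are affected, and the pooled tables do not change. The documents do not support a claim that the safety conclusions as a whole would be wrong. The correction is still worth making, because these columns bear on tolerability by dose.

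**What to change.** In SAP 7.8.1:
1. Base maintenance-period percentages in both split tables on Treated Set patients with at least one dose on or after Visit 26 (Week 24), and print that N in each column, for planned and actual treatment.
2. Keep the Treated Set denominator for the escalation and pooled columns.
3. Assign residual-effect-period events in patients who stopped during escalation to the escalation period, so that numerator and denominator cover the same patients.
4. Footnote that the maintenance columns are conditional on having completed escalation and are not a comparison of the groups as randomised.

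The cost is a few lines of SAP text and one programming flag, which the disposition and shift tables already need. The small downside is the conditioning that the footnote declares.

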#### 3.3.4.2 Withdrawal of consent to trial participation

Patients may withdraw their consent to trial participation at any time without the need to justify the decision.

If a patient wants to withdraw consent, the Investigator should be involved in the discussion with the patient and explain the difference between trial treatment discontinuation and withdrawal of consent to trial participation, as well as explain the options for continued follow-up after trial treatment discontinuation, please see [Section 3.3.4.1](#) above.

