### **6.2.3 Follow-up period and trial completion**

The patients should make all efforts to complete the trial including the 4-week follow-up period which extends from Visit 32 until Visit 33. The residual effect period (REP) of 28 days will be fully covered by the period between the last administration of the trial medication and the end of the follow-up period. Procedures to be completed at the Follow-up visit (Visit 33) can be found in the [Flow Chart](#). The sequence of the procedures will be the same as in the treatment period. With the conduct of Visit 33 the observation period has ended. Trial completion should be recorded on the corresponding eCRF page.

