6. GENERAL ANALYSIS DEFINITIONS

6.1 TREATMENT(S)

6.1.1 Study Phases

The following summarises the study phases defined in the protocol for a patient who completes all visits and remains on treatment as planned:

Table 6.1.1: 1 Study phases

| Study Phase Description | Start | End |
|-----------------------------------|------------------------------|--|
| Screening phase | Date of informed consent | Day before Visit 2 (Week 0) |
| Treatment phase – dose escalation | Date of Visit 2 (Week 0)* | Day before Visit 26 (Week 24) |
| Treatment phase – maintenance | Date of Visit 26 (Week 24) | Date of Visit 32 (Week 48) |
| Follow-up phase | Day after Visit 32 (Week 48) | Date of end of study participation (expected to be 4 weeks after Visit 32 (Week 48)) |

* See also baseline definitions in [Section 6.7](#).

Patients who discontinue treatment early are not required or expected to complete the planned treatment phase. The follow-up phase is defined in the protocol as up to 4 weeks after the end of the planned treatment phase for patients who completed treatment, or 4 weeks after the End of Treatment visit for patients who discontinued early. It is not therefore expected that there will be a significant amount of data captured in this trial for any patients which is more than about a month after stopping treatment.

The follow-up period will not exist for any randomised patient who was lost to follow-up whilst still receiving treatment.

The definition of on-treatment for analysis purposes is given in [Section 6.1.6](#). The use of a residual effect period (REP) means that data captured during the follow-up period specified in the protocol could be assigned to the treatment period for analysis.

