6.1.6 Definition of On-Treatment

There is no continued study participation for patients who have discontinued treatment early. Consequently off-treatment data capture is expected to be restricted to those data captured during the safety follow-up period specified by the CTP, although there may be occasional unplanned exceptions to this.

Even for patients who completed treatment according to the protocol, data captured during the follow-up period may be relevant for safety.

It is important to be clear whether all available data will be used in a particular summary or analysis, or whether only on-treatment data will be used. The definition of “on-treatment” for this purpose is as described below, and it includes any temporary treatment interruptions which might occur prior to last dose of study treatment. It is assumed that all patients will have a date of last administration of study medication accurately recorded on the End of Treatment eCRF page.

“Off-treatment” refers to data which are captured after baseline but which are not “on-treatment” as defined below.

Safety

An AE start date or other safety assessment date will be considered “on-treatment” if the AE start date or assessment date is between the date of first dose and 28 days after the date of last

dose of study treatment inclusive (the residual effect period (REP) is defined as 28 days in this trial).

The same on-treatment definition will be used for all types of safety data.

Efficacy

All post-baseline efficacy data (including for exploratory biomarkers) will use the same 28-day definition of “on-treatment” as for safety, where on-treatment analyses are specified (as opposed to those efficacy analyses which use all data, both on- and off-treatment).

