An additional table will present the frequency of patients with AEs by worst CTCAE grade (1 to 5) and by primary SOC and PT. When no events meet the criteria for inclusion, the table will be shown as indicating no events of that type have occurred.

The following tables will be produced separately by baseline body weight subgroup (< 100 / ≥ 100 kg) and by presence of diabetes (yes/no):

- Overall AE summary
- Summary of all AEs by primary SOC and PT
- Summary of AEs leading to treatment discontinuation by primary SOC and PT.

For disclosure of AE data on ClinicalTrials.gov, the frequency of patients with non-serious AEs occurring with an incidence of greater than 5% (PT occurring in more than 5% of treated patients in one or more treatment groups) will be summarised by treatment, primary SOC and PT. The frequency of patients with serious AEs and drug related serious AEs will also be summarised respectively.

For disclosure of AE data in the EudraCT register, the frequency of patients with AEs, the frequency of patients with non-serious AEs with an incidence of greater than 5% (as above) and the frequency of patients with serious AEs will be summarised. Furthermore, the total number of treated patients by country and by age group will be summarised.

An exposure-adjusted summary of all AEs by primary SOC and PT will also be produced. For this purpose, the time at risk will be defined for specific AEs as follows:

- For patients with no events, the time at risk is the number of days on-treatment (inclusive), as defined in [Section 6.1.6](#)
- For patients with one or more event, the time at risk is the number of days from the start of treatment to the start of the first on-treatment event (inclusive).

The total time at risk (years) for a treatment group is the sum of the individual patient times at risk for that treatment group (days) divided by 365.25. Multiple occurrences of the same event for a particular patient will not be counted as separate events in this summary; a patient will either be considered to have no events of the type being summarised, or to have one or more occurrences of that event.

A frequency table will be produced of symptoms of injection site reaction (swelling, induration, heat, redness, pain, other) for the subset of patients with the event.

Additional trial-specific information captured in the eCRF for Grade 3 nausea will be listed only and not summarised.

Adverse Events of Special Interest (AESIs)

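### SAP 7.8.1 states no cap at death or end of participation on time at risk, so exposure-adjusted AE rates may be slightly understated

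*SAP*

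**What the plan says.** SAP 7.8.1 (Adverse Events) plans an exposure-adjusted summary of all AEs by system organ class and preferred term. The denominator for an arm is the sum of the individual times at risk, and there are two rules:

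- Without the event: "For patients with no events, the time at risk is the number of days on-treatment (inclusive"), with a reference to SAP 6.1.6.
- With the event: "the time at risk is the number of days from the start of treatment to the start of the first on-treatment event (inclusive").

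Under SAP 6.1.6 a safety record is on-treatment if its date "is between the date of first dose and 28 days after the date of last" dose, and "the residual effect period (REP) is defined as 28 days in this trial". Neither section shortens this for death, withdrawal or last contact.

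Four other places bear on whether those 28 days are observed:

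- SAP 6.1.1 closes the follow-up phase when study participation ends, and adds: "The follow-up period will not exist for any randomised patient who was lost to follow-up whilst still receiving treatment".
- Protocol 3.3.4.2: "Patients may withdraw their consent to trial participation at any time without the need to justify the decision".
- Protocol 5.2.6.2.1 has AEs entered in the eCRF up to the individual patient's end of trial. After that there is no active monitoring, and the few events still reportable go on the SAE form only.
- Protocol 6.2.3 says that the residual effect period "will be fully covered by the period between the last administration of the trial medication and the end of the follow-up period".

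**The concern.** A rate per patient-year is interpretable only if an event occurring on any counted day could have been recorded. For a patient who is lost, withdraws consent or dies soon after the last dose, AE collection has closed, yet the rule read literally keeps counting to day 28. Those days carry no possible event, so they can only lower the rate. The event rule does not offset this, because it stops at the first event. Time at risk is set separately for each AE term, and for most terms most patients have no event, so the uncapped rule governs most of the denominator.

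At stake is the accuracy of a table whose purpose is to adjust for unequal follow-up. If the proportion leaving observation differs between arms, the comparison of rates shifts slightly too.

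**Working it through.** The documents state no exposure-adjusted rate, person-time total or loss rate, so there is no figure of the plan's own to reproduce. The check is person-time arithmetic.

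**Inputs from the documents.** Visit 32 is on day 337 and Visit 33 follows 28 days later (protocol Flow Chart). The last dose is one week before Visit 32 (protocol 6.2.2). The residual effect period is 28 days (SAP 6.1.6). Planned group size is 60 (protocol 7.5).

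**Assumptions.** A share p of the arm is lost, with observation ending on the day of the last dose, t. All other patients complete. Nobody in the arm has the event (a rare term).

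**1. Is the tail observed for those who attend Visit 33?** For completers, last dose = 337 − 7 = day 330, end of the residual effect period = 330 + 28 = day 358, and Visit 33 = 337 + 28 = day 365. That gives 35 days of observation after the last dose, so the statement in protocol 6.2.3 is correct. Patients who stop early and attend are covered too: their Visit 33 is 28 days after an early-discontinuation visit that itself follows the last dose.

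**2. One affected patient, worst case.** Credited time is t + 28 against t observed.

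- t = day 57 (Week 8): 85 against 57, 85/57 − 1 = 49%.
- t = day 113 (Week 16): 141 against 113, 141/113 − 1 = 25%.

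**3. Arm level.** Overstatement of time at risk = 28p / [(1 − p) × 358 + p × t].

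| p | t = 57 | t = 113 |
|---|---|---|
| 3% | 0.84/348.97 = 0.24% | 0.84/350.65 = 0.24% |
| 10% | 2.80/327.90 = 0.85% | 2.80/333.50 = 0.84% |
| 20% | 5.60/297.80 = 1.88% | 5.60/309.00 = 1.81% |

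An overstatement x of the denominator lowers the rate by x/(1 + x), so 1.88% becomes 1.85%.

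**4. A rate.** Take 60 patients, p = 10% and t = day 78. Observed time is 54 × 358 + 6 × 78 = 19,800 days = 54.21 patient-years. The uncapped rule adds 6 × 28 = 168 days, giving 54.67 patient-years. Three events then give about 5.49 instead of 5.53 per 100 patient-years (the shorter time of the three patients with events is ignored).

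**5. Between arms.** The factor applied to each arm's rate is observed time divided by credited time, here with t = day 50.

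- 15% lost: 311.80/316.00 = 0.9867. 2% lost: 351.84/352.40 = 0.9984. The rate ratio is multiplied by 0.988.
- 30% lost against 5% lost: the rate ratio is multiplied by about 0.973.

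**The case against.** The strongest reply is that SAP 6.1.6 classifies dated records as on- or off-treatment and does not set out to define person-time. SAP 6.1.1 ends follow-up with study participation and says that patients lost on treatment have no follow-up period, so one could hold that no residual-effect days exist for them. Programming may truncate anyway, and protocol 7.2.5 bases safety analyses on sponsor standards that might say so. Part of this stands: no sentence states that a lost, withdrawn or dead patient is credited with 28 days. That follows only from a literal reading. But SAP 7.8.1 does turn the 6.1.6 window into a number of days, the limit in 6.1.1 is carried into neither section, and the sponsor standards are not available to check.

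Three stronger readings are tempting and not supported.

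- A reader might infer that the bias grows with early treatment discontinuation. It does not: patients who stop early are directed to Visits 32 and 33, and those who attend are observed over the whole 28 days. Only loss from observation matters.
- A reader might take 49% or 25% as the size of the bias. These are worst cases for one patient whose observation stops on the day of the last dose, and no per-patient rate is reported.
- A reader might see a contradiction in SAP 7.7, which leaves the residual effect period out of total patient-years. That total measures drug exposure, a different quantity. Using the 28-day window both to count AEs and to set time at risk is coherent where the days are observed.

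The objection on size also stands. The exact Poisson 95% interval for 3 events runs from about −79% to +192%, against which a move from 5.49 to 5.53 cannot be seen.

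**Conclusion.** The point holds as a minor gap in the definition. Followed as written, the rule lets unobserved days into the denominator for patients who leave observation within 28 days of the last dose and did not have the event in question. The direction is certain: the rate for any term can only be lowered. The size rests on an assumed loss of 3% to 20%, loss on the day of the last dose around Weeks 8 to 16, and full follow-up for everyone else. Loss some days after the last dose would reduce it. SAP 7.8 plans no safety hypothesis test, so no formal conclusion of the trial depends on this table.

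**What to change.** In SAP 7.8.1, define time at risk for patients without the event as the days from first dose to the earliest of (a) last dose + 28 days, (b) end of study participation and (c) death, inclusive. Leave the rule for patients with an event, and the on-treatment definition in SAP 6.1.6, unchanged.

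The cost is one sentence and about one line of code. No new data are needed: SAP 6.1.1 already uses the end of study participation to close follow-up, SAP 7.7 already tabulates duration on study, and deaths are recorded. The only consequence is slightly higher exposure-adjusted rates.
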